## 6.5 Concomitant medications

In the absence of contraindication, the concomitant use of the following medications is recommended; proton pump inhibitors for peptic ulcer prophylaxis, bisphosphonates, vitamin D preparations, and calcium preparations for osteoporosis prophylaxis, and trimethoprim-sulfamethoxazole for Pneumocystis pneumonia prophylaxis. In addition, premedication is administered at the time of rituximab administration (see **6.1**).

#### **6.6 Restrictions**

There are no daily life restrictions required for participants of this study. However, an appropriate use of contraception methods for 12 months after the final dose of rituximab. Participants are also recommended to avoid vaccination with live vaccine while receiving rituximab.

## 7. Clinical assessments, Laboratory evaluations, and Schedule

## 7.1 Screening

After patient's written consent was obtained, the following clinical assessments and laboratory evaluations are performed.

- Patient background (subject identification code, age at the time of consent, year and month of birth, sex, body height, diagnosis, date of diagnosis, medical history, complication)
- · Body weight
- Vital signs (blood pressure, pulse, body temperature)
- Chest X-ray
- · Electrocardiography (ECG)
- · Blood tests:

Serum creatinine level; MPO-ANCA and PR3-ANCA measured by ELISA, CLEIA, or FEIA; HIV antibodies; HBs antigen/antibodies; HBc antibodies; and HCV antibodies

- Pregnancy test1)
- · Observation of adverse events

• Presence or absence of prednisolone administration during the period from screening to patient enrollment, and the dosage if it was used

Note that following data obtained within 2 weeks before the consent can be used; chest X-ray, ECG,

MPO-/PR3-ANCA, HIV antibodies, HBS antigen/antibodies, HBc antibodies, and HCV antibodies. 1) A urine pregnancy test will be performed (hCG  $\geq$ 25 IU/L).

## 7.2 Clinical assessments and laboratory evaluations during the study period

During the study period, the following clinical assessment and laboratory evaluations are performed as specified for each evaluation time point (at 0, 1, 2, 4, 6, 9, 12, 18, and 24 months, and when a relapse is confirmed; \* 0 month = day  $1\pm 3$  days, 1 month = day  $30\pm 7$  days, 2 months = day  $60\pm 15$  days, 4 months = day  $120\pm 15$  days, 6 months = day  $180\pm 15$  days, 9 months = day  $270\pm 30$  days, 12 months = day  $360\pm 30$  days, 18 months = day  $540\pm 30$  days, 24 months = day  $720\pm 30$  days). During the maintenance treatment period (from month 6 to month 18), interval of hospital visits should not exceed 3 months at a maximum.

- · Confirmation of medication adherence
- · Confirmation of concomitant medications

• Presence or absence of additional treatment for ANCA-associated vasculitis not included in study protocol

- · Observation of adverse events
- Body weight
- Vital signs (blood pressure, pulse, body temperature)
- Blood tests:

<Blood cell count> Red blood cells, hemoglobin, platelets, white blood cells, differential leukocyte counts, number of B cells

<Serum biochemical examinations> Total protein, albumin, electrolytes [Na, K, Cl], BUN, serum creatinine level, CPK, total bilirubin level, AST, ALT, ALP, LDH, γ-GTP, CRP, Ig-G, Ig-A, Ig-M, C3, C4, complement titer, T-Cho, LDL-C, HDL-C, TG, blood glucose, HbA1c, and MPO-ANCA and PR3-ANCA measured by ELISA (or CLEIA, FEIA)

Note that MPO-ANCA and PR3-ANCA data at the time of screening can be used as substitutes for data at 0 months.

• Urinary examinations: General urine tests (glucose, protein, occult blood), urinary sediment, urinary creatinine

- BVAS ver3
- VDI (at 0, 6, 12, 18, and 24 months only)
- SF-36 (at 0, 6, 12, 18, and 24 months only)
- $\cdot$  VAS

• Bone density of the lumbar spine (at 0, 12, and 24 months; images taken during day 1–28 are acceptable as 0-month data.)

- Pregnancy test1)
- Confirmation of survival, ESRD, remission or relapse
- 1) A urine pregnancy test will be performed (hCG  $\geq$ 25 IU/L).

## 7.3 Clinical assessments and laboratory evaluations at completion or discontinuation of the study

The following tests are performed as specified at the end of the study or when the study is discontinued.

- Confirmation of medication adherence
- Confirmation of concomitant medications
- Presence or absence of additional treatment for ANCA-associated vasculitis not included in study protocol
- · Observation of adverse events
- Body weight
- Vital signs (blood pressure, pulse, body temperature)
- Blood tests:

<Blood cell count> Red blood cells, hemoglobin, platelets, white blood cells, differential leukocyte counts, number of B cells

<Serum biochemical examinations> Total protein, albumin, electrolytes [Na, K, Cl], BUN, serum creatinine level, CPK, total bilirubin level, AST, ALT, ALP, LDH, γ-GTP, CRP, Ig-G, Ig-A, Ig-M, C3, C4, complement titer, T-Cho, LDL-C, HDL-C, TG, blood glucose, HbA1c, and MPO-ANCA and PR3-ANCA measured by ELISA (or CLEIA, FEIA)

• Urinary examinations: General urine tests (glucose, protein, occult blood), urinary sediment, urinary creatinine

- BVAS ver3
- VDI
- SF-36
- $\cdot$  VAS

• Bone density of the lumbar spine (at 0, 12, and 24 months; images taken during day 1–28 are acceptable as 0-month data.)

- Pregnancy test
- · Confirmation of survival, ESRD, remission or relapse

1) A urine pregnancy test will be performed (hCG  $\geq$ 25 IU/L).

## 7.4 Pregnancy test (only for women of childbearing potential)

Female patients of childbearing potential undergo pregnancy tests (urinary tests: hCG  $\geq$ 25 IU/L) at the following time points. The principal investigator or co-investigators confirm that the pregnancy test is negative during the period from consent to initiation of administration of the study medication. When a false positive or positive result is obtained, the test should be repeated in accordance with the package insert of the extracorporeal diagnostic agent, and report the result to a gynecologist. The principal investigator or co-investigators also confirms that the pregnancy test results are negative at the end of the study and when the study is discontinued.

- (1) Before starting the study medication
- (2) At the end of the study or when the study is discontinued
- (3) 4 weeks after the completion or discontinuation of the study

## 7.4.1 Definition of women of childbearing potential

Women who do not meet any of the following criteria

- (1) Women who have reached natural menopause (45 years of age or older and no menstruation experienced for 1 year or more)
- (2) Women who have undergone hysterectomy
- (3) Women who have undergone bilateral oophorectomy

#### 7.5 Tests and observation items for efficacy assessment

#### 7.5.1 Proportion of participants who achieved remission (at 6 months)

The proportion of study subjects who achieved remission at 6 months will be evaluated.

# 7.5.2 Time to remission, overall survival period, relapse-free period, time to ESRD, and time to the first serious adverse event

The number of days from randomization to each of abovementioned events will be evaluated.

7.5.3 Occurrence rate of death, relapse, ESRD, serious adverse events, and composite outcome of those (at 6 and 24 months; \* at 6 months, occurrence rate of death, ESRD, and serious adverse events only)

The number of occurrence and proportion of those events are used for evaluation.

## 7.5.4 Occurrence rate of minor and major relapses (at 24 months)

The number of occurrence and proportion of minor and major relapses are used for evaluation.

## 7.5.5 Disease activity assessment (at 6 and 24 months)

BVAS ver3 is used for assessments.

#### 7.5.6 Irreversible disorder assessment (at 24 months)

VDI is used for assessments.

## 7.5.7 Cumulative glucocorticoid dose (at 6 and 24 months)

Cumulative glucocorticoid doses from the beginning of study participation to 6 and 24 months are evaluated.

## 7.5.8 Patient general assessment (at 6 and 24 months)

VAS is used for assessments.

#### 7.5.9 Patient QOL assessment (at 6 and 24 months)

SF-36 is used for assessments.

## 7.6 Tests and observation items for safety assessment

## 7.6.1 Determination of adverse events

An adverse event refers to any unfavorable or unintended sign (including an abnormal laboratory finding), symptom, or disease that occurs in patients administered a study medication, regardless of whether it has a causal relationship with the trial medication.

As a general rule, an adverse event is itemized and graded using the Common Terminology Criteria for Adverse Events (CTCAE ver 4.0). Adverse events defined in this study include events occurred during a period from patient's consent to commencement of study medication.

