## 6. Study Procedures

Patients participating in the study will receive administration of 375 mg/m^2 of rituximab once weekly  $\times$  4 times along with glucocorticoids, as remission induction treatment. Participants are randomly assigned to either the high-dose glucocorticoid group (conventional treatment group) or low-dose glucocorticoid group (novel treatment group) at 1:1 ratio. At the time of randomization, study subjects are stratified according to age, renal function, and ANCA subtype.

Defining the day of glucocorticoid commencement as day 1, the first dose of rituximab will be given between day 1 and day 7. The first dose of glucocorticoids is to be given on the day of patient enrollment or the following day. However, with respect to glucocorticoids, administration of prednisolone 0.5 mg/kg/day is allowed during the period from screening to patient enrollment (up to 7 days) depending on physicians' discretion.

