## 8. Management and Report in Case of Adverse Events

## 8.1 Definition of adverse event

An adverse event refers to any unfavorable or unintended sign (including an abnormal laboratory finding), symptom, or disease that occurs after the trial participation, regardless of whether it has a causal relationship with the trial medication. Adverse events occurred by the completion date of the trial medication administration will be observed until 4 weeks after the final administration. When the adverse event persists, the observation should be continued beyond 4 weeks until recovery, wherever possible. Even if an adverse event occurs after the completion of trial medication administration, follow-up observation shall be continued wherever possible in case the causal relationship with the trial medication cannot be denied. However, this is not applied in following cases; symptoms have become chronic due to exacerbation of primary disease or complications, or follow-up observation is difficult due to transferring to another hospital or commencement of a post-trial treatment.

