## 9.2 Secondary endpoints

## [Efficacy]

- 1 Time to remission
- ② Overall survival period, relapse-free period, time to ESRD, time to the first serious adverse event These endpoints are defined as a length of time from the time of randomization to the occurrence of respective events, and patients who did not experience the event will be counted as censored. Definitions of event and date censored for each endpoint are shown in a table below.

Endpoint	Event (whichever is	Date censored	Competing risk
	earlier if more than one)		
Time to remission	Remission	The last day of confirmed	Death
		absence of remission	
Overall survival period	Any death	The last day of confirmed	None
		survival	
Relapse-free survival	Any death, relapse	The last day of confirmed	None
period		absence of relapse	
Time to ESRD	ESRD	The last day of confirmed	Death

		absence of ESRD	
Time to the first serious	First serious adverse event	The last day of confirmed	None
adverse event	(including death and	absence of serious adverse	
	hospitalization)	event	

- ③ The proportion of death, relapse, ESRD, or serious adverse events, and proportion of a composite outcome thereof (at 6 and 24 months; \*at 6 months, proportions of death, ESRD, and serious adverse events only)
- ④ Proportions of minor and major relapses (at 24 months)
- (5) The proportion of participants who achieved remission and glucocorticoid cessation
- (6) Assessment of disease activity using BVAS ver3 (at 6 and 24 months)
- ⑦ Irreversible damage measured using VDI (at 24 months)
- 8 Evaluation of health-related QOL using SF-36 (at 6 and 24 months)
- 9 Patient general assessment with a VAS (at 6 and 24 months)
- (1) Cumulative glucocorticoid dose (at 6 and 24 months)

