## [Safety]

- ① The number of occurrence and proportion of adverse events and serious adverse events that occurred (at 6 and 24 months)
- 2 Proportions of new-onset diabetes, hypertension, and dyslipidemia requiring treatment (at 6 and 24 months)
- ③ Proportion of sleep disorder requiring treatment (at 6 and 24 months)
- ④ Proportion of pathological fractures and bone density of the lumbar spine (at 24 months)
- (5) The number of occurrence and proportion of infections (intravenous or oral antibiotics are used) (at 6 and 24 months)

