#### 10.5.2.3 Secondary safety endpoint analyses

This study is a non-inferiority trial, in which adverse effects of glucocorticoids are expected to be reduced in the low-dose group. The adjustment of multiplicity will not be performed in the analyses on the secondary safety endpoints. The significance level in the hypothesis test will be 5% (two-sided), and confidence intervals to be calculated are two-tailed 95% confidence intervals.

The number of cases in which adverse events and serious adverse events occurred and proportions of those with and without occurrence, etc. are aggregated in a group-by-group manner, and Pearson's chi-square test will be used for intergroup comparisons (or Fisher's exact test, when cells with an expected frequency less than 5 account for 20% or more).

For occurrence of new-onset diabetes requiring treatment, hypertension, dyslipidemia, sleep disorder

requiring treatment, pathological fractures, and infections (intravenous or oral antibiotics are used), the number of cases and proportions of cases with and without occurrence in each group are determined, and Pearson's chi-square test will be used for intergroup comparisons (or Fisher's exact test, when cells with an expected frequency less than 5 account for 20% or more).

For bone density of the lumbar spine, the data will be aggregated using summary statistics for each group, and compared between the groups by the analysis of variance model.

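### The adverse event definition reaches back to consent and the between-arm AE and SAE comparisons fix no start point for counting (minor)

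*Protocol*

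**What the plan says.** The protocol describes the study's adverse events in three ways.

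- Section 7.6.1, first sentence: a sign, "symptom, or disease that occurs in patients administered a study medication".
- Section 7.6.1, last sentence: "Adverse events defined in this study include events occurred during a period from" consent until study medication starts.
- Section 8.1: an event that "occurs after the trial participation, regardless of whether it has a causal relationship with the trial medication".

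Section 7.6.2 defines a serious adverse event as an adverse event meeting one of its criteria, so SAEs inherit whichever window applies. Section 9.2 lists AE and SAE numbers and proportions at 6 and 24 months as safety endpoints and gives no start point. Section 10.5.2.3 aggregates by arm "The number of cases in which adverse events and serious adverse events occurred and proportions of those with and without occurrence" and compares arms by chi-square or Fisher's exact test at a two-sided 5% level. The safety analysis set in section 10.1.3 selects patients by dosing. It does not select events by onset date.

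For time to first SAE, section 9.2 does fix an origin: "These endpoints are defined as a length of time from the time of randomization to the occurrence of respective events".

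**The concern.** The three descriptions start the clock at three places: dosing, consent and trial participation. The one that reaches furthest back is worded as part of the definition. If the comparisons use that definition as written, an event in the screening week counts against an arm that had not yet been allocated.

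That week is unlikely to be free of events. Patients have newly diagnosed, active vasculitis. Section 6 lets them take prednisolone 0.5 mg/kg/day for up to 7 days before enrolment. Abnormal laboratory findings count as AEs, and prolonged hospitalisation counts as an SAE.

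An early event also uses up the patient's binary outcome, because a patient already classed as having had an event contributes nothing more to the contrast. The bias is towards no difference. Section 10.5.2.3 expects fewer glucocorticoid harms in the low-dose arm, and that expected benefit is what a non-inferior remission rate would be weighed against. Separately, the SAE proportion and time to first SAE could rest on different sets of events.

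**Working it through.** **The protocol's own figure.** The only power calculation is for the primary endpoint: remission 0.80 in each arm, margin 0.2, one-sided α 0.025, power 0.80.

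n per arm = (0.16 + 0.16)(1.960 + 0.842)² / 0.2² = 62.8, rounded up to 63. With 10% withdrawal, 63 / 0.9 = 70 per arm, 140 in total. This reproduces, and the present point does not touch it. No power is stated for the AE or SAE tests.

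**Inputs for the safety contrast.** From the protocol: 70 per arm (sections 3.1 and 10.2) and a two-sided 5% test (section 10.5.2.3). Assumed, because the protocol gives neither: the true proportions after allocation, p, taken as 35% (high dose) and 15% (low dose), and the share q of patients with an event before allocation, taken as equal in both arms and unrelated to later risk.

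**Dilution.** A patient is a case after an early event or a later one:

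p′ = q + (1 − q)p, so p′(high) − p′(low) = (1 − q)[p(high) − p(low)].

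**Power.** Φ((d − 1.96·SE₀)/SE₁), with d the diluted difference, SE₀ the pooled and SE₁ the unpooled standard error.

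- q = 0: d = 0.20, SE₀ = √(0.25 × 0.75 × 2/70) = 0.0732, SE₁ = √((0.2275 + 0.1275)/70) = 0.0712. Then (0.20 − 0.1435)/0.0712 = 0.794, power 78.6%.
- q = 5%: d = 0.19, SE₀ = 0.0765, SE₁ = 0.0748. Then (0.19 − 0.1499)/0.0748 = 0.535, power 70.4%.

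| q | High | Low | Difference | Power |
|---|---|---|---|---|
| 0 | 35.0% | 15.0% | 20.0 points | 78.6% |
| 1% | 35.7% | 15.9% | 19.8 | 77.0% |
| 2% | 36.3% | 16.7% | 19.6 | 75.3% |
| 5% | 38.3% | 19.3% | 19.0 | 70.4% |
| 10% | 41.5% | 23.5% | 18.0 | 62.5% |

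**Other assumed rates**, power at q = 0, 2%, 5% and 10%:

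- 40% v 20%: 73.8%, 70.9%, 66.7%, 59.9%
- 30% v 15%: 56.7%, 53.0%, 48.1%, 41.2%
- 90% v 75% (a pattern that might fit any AE): 64.9%, 63.8%, 62.2%, 59.4%

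**How large q might be.** Section 23.1 puts screening within one week. Section 6 starts glucocorticoid on the day of enrolment or the next day. Seven days is 7/180 = 3.9% of the 6-month period and 7/720 = 1.0% of the 24-month period. This sets a scale and does not estimate q, since event rates need not be constant.

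**Which part of the window dilutes.** Section 5 lists only rituximab as a study medication, and section 6 allows its first dose on day 1 to day 7 of glucocorticoid. If study medication means rituximab, events from day 1 to the first infusion fall inside the window but occur on the allocated glucocorticoid dose. They belong in the contrast. Only events before allocated treatment dilute it.

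**The case against.** The strongest reply is that section 7.6.1 sits under tests and observation items and may be no more than a rule for what to record. Recording AEs from consent is ordinary practice. No sentence says that these events enter the between-arm tests, section 10.5 leaves further detail to the SAP, and a treatment-emergent rule is commonly placed there. Visit times also run from day 1, which hints at a day-1 clock for the 6- and 24-month proportions.

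Much of this stands. A reader might infer that the protocol orders pre-treatment events into the comparisons. It does not say so. They enter only if the stated definition is applied literally, and the SAP may exclude them. The point survives because the protocol states an inclusive definition, contradicts it twice, and attaches no start date to the comparisons that use it. An SAP restriction would have to narrow the stated definition.

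A reader might also infer that the whole toxicity comparison is compromised. Section 7.6.5 already limits diabetes, hypertension, dyslipidaemia, sleep disorder, fractures and infections to new conditions needing treatment, so the dilution concerns mainly the overall AE and SAE tests. What remains for those items is that no date is given against which a condition is new.

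Finally, the mismatch with time to first SAE arises only if the SAE proportion counts SAEs before randomisation. It shares the same condition.

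**Conclusion.** A minor defect, held with moderate confidence. The inconsistency between the AE descriptions and the absent start point are plain in the text. The dilution is conditional on a literal reading.

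Over the rates tried, q of 1% to 5% costs between under 1 and about 9 power points. At 35% v 15% it costs about 2 to 8. The larger loss at q = 10%, about 16 points at those rates, would need one patient in ten to have an event in a window of about a week, and nothing in the protocol supports or excludes that. The stronger conclusion, that a real safety difference would be hidden, is therefore not supported.

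The tests affected are secondary and carry no multiplicity adjustment. The primary endpoint is unaffected. All power figures rest on assumed arm rates, on q being equal in both arms, and on early events being unrelated to later risk.

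**What to change.** Keep recording events from consent. Then:

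1. In sections 7.6.1 and 10.5.2.3, state that between-arm AE and SAE counts, proportions and tests include only events with onset, or worsening in grade, on or after the first allocated glucocorticoid dose (day 1). Do not use the first rituximab dose as the cut, because it may fall up to day 7.
2. List earlier events separately by arm, without a test.
3. Use the same event set for the SAE proportion and for time to first SAE. Randomisation can precede day 1 by up to a day, so say that an SAE in that gap is listed and counted in neither.
4. Make day 1 the reference date for new conditions in section 7.6.5.
5. Align the wording of sections 7.6.1 and 8.1, and say what study medication means there.

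The cost is a few sentences. Section 8.2 already puts the date of occurrence and CTCAE severity on the case report form. Worsening needs its own dated entry if the form holds one grade per event, which the protocol does not say. No safety information is lost.

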## 7.6.2 Serious adverse events

A serious adverse event refers to an adverse event that meets any of the following criteria [16].

- (1) Death
- (2) Life-threatening
- (3) Resulting in disability
- (4) Risks leading to disability
- (5) Requiring inpatient hospitalization or prolongation of existing hospitalization
- (6) Serious condition according to the above (1) (5)
- (7) Congenital diseases or anomaly in a later generation

#### 7.6.3 Non-serious adverse events

Non-serious adverse events are adverse events other than those that have been determined to be "serious," and the judgment shall be made by the principal investigator or co-investigators.

#### 7.6.4 Reversibility of adverse events and causal relationships with glucocorticoids

Recovery of adverse event means recovery to a condition where the adverse event no longer exists or to the pre-treatment grade. The judgement of causality between an adverse event and trial medication/glucocorticoids will be performed based on the subject's general condition, complications, concomitant medications/treatments, and temporal relationships. The causality judgement shall be either "deniable" or "undeniable."

